9.4 Records Retention

These will include subject case histories and regulatory documents. These will include subject case histories and regulatory documents. These will include subject case histories and regulatory documents. There will be a subject code master list that will be stored so as to protect subjects' confidentiality. Case Report Forms will be coded. There will be no subject names or other directly identifiable information will not appear on any reports, publications, or other disclosures of clinical study outcomes.

The sponsor-investigator will retain the specified records and reports for;

- 1. Up to 2 years after the marketing application is approved for the drug; or, if a marketing application is not submitted or approved for the drug, until 2 years after shipment and delivery of the drug for investigational use is discontinued and the FDA has been so notified. OR
- 2. As outlined in the Mayo Clinic Research Policy Manual

Whichever is longer

10 Study Monitoring, Auditing, and Inspecting

10.1 Study Monitoring Plan

The investigator will allocate adequate time for such monitoring activities. The Investigator will also ensure that the monitor or other compliance or quality assurance reviewer is given access to all the study-related documents and study related facilities (e.g. pharmacy, diagnostic laboratory, etc.), and has adequate space to conduct the monitoring visit.

10.2 Auditing and Inspecting

The investigator will permit study-related monitoring, audits, and inspections by the IRB, the sponsor, and government regulatory agencies, of all study related documents (e.g. source documents, regulatory documents, data collection instruments, study data etc.). The investigator will ensure the capability for inspections of applicable study-related facilities (e.g. pharmacy, diagnostic laboratory, etc.).

Participation as an investigator in this study implies acceptance of potential inspection by government regulatory authorities and applicable compliance offices.

11 Ethical Considerations

This study is to be conducted according to United States government regulations and Institutional research policies and procedures.

This protocol and any amendments will be submitted to a properly constituted local Institutional Review Board (IRB), in agreement with local legal prescriptions, for formal approval of the study. The decision of the IRB concerning the conduct of the study will be made in writing to the sponsor-investigator before commencement of this study.

All subjects for this study will be provided a consent form describing this study and providing sufficient information for subjects to make an informed decision about their participation in this study. This consent form will be submitted with the protocol for review and approval by the IRB for the study. The formal consent of a subject, using the Approved IRB consent form, must be obtained before that subject undergoes any study procedure. The consent form must be signed by the subject or the subject's legally authorized representative, and the individual obtaining the informed consent.

12 Study Finances

12.1 Funding Source

Bristol Myers Squibb and Company is funding this research study.

Appendix:

Physician Global Assessment: 12,13

Grade 0 Completely clear: no evidence of disease (100% improvement) CCR

Grade 1 Almost clear: very significant clearance (≥90% to <100%) PR

Grade 2 Marked Improvement: significant improvement (≥75% to <90%) PR

Grade 3 Moderate improvement: intermediate between slight and marked (≥50% to <75%) PR

Grade 4 Slight improvement: some improvement (≥25% to <50%); however, significant evidence of disease remains SD

Grade 5 No change; disease has not changed from baseline condition (+/-<25%) SD

Grade 6 Worse, disease is worse than at baseline evaluation by (≥25%) or more PD

CCR- Complete clinical response

PR- Partial response

SD- Stable disease

PD- Progressive Disease

Lichen Planopilaris Activity Index

LPPAI score (0–10) is calculated as follows: (pruritus + pain + burning)/3+ (scalp erythema + perifollicular

[figure not shown]
erythema + perifollicular scale)/3 + 2.5 (pull test) +1.5 (spreading/2).

LPPAI	0 (Absent)	1 (Mil	d) 2	(Moderate)	3 (Severe)
Symptoms					
Pruritis					
Pain					
Burning					
Signs					
Erythema					
Perifollicular					
erythema					
Perifollicular					
keratosis					
Pull Test		0 (negative)		1 (positive	e)
Spreading of Disease 0 (no s		preading)	1 (indetermi	nate) sp	preading

Itch-

Numerical Rating Scale (NRS) (bottom)- 14,15

- 0- No itch
- 1-4 Mild itch
- 4-7 Moderate itch
- 7-9 Severe itch
- 10- Very severe itch

Pruritus Verbal Rating Scale (VRS)

On average,	please	rate your	itch over	the past	24 hours:
--------------------	--------	-----------	-----------	----------	-----------

- □ 0 (None)
- □ 1 (Mild)
- □ 2 (Moderate)
- □ 3 (Severe)

At its worst, please rate your itch in the last 24 hours:

- □ 0 (None)
- □ 1 (Mild)
- □ 2 (Moderate)
- □ 3 (Severe)

Pruritus Visual Analogue Scale

Please rate your **average** itch level over the past day by placing a vertical mark on the line below.

No Itch Worst Imaginable Itch

____.__cm

Please rate your **worst** itch level over the past day by placing a vertical mark on the line below.

No Itch			Worst Imaginable Itch
	1	I	
			cm

VAS score interpretation:

VAS 0 = No itch

VAS < 3 = Mild itch

 $VAS \ge 3 < 7 = Moderate itch$

 $VAS \ge 7 < 9 = Severe itch$

 $VAS \ge 9 = Very severe itch$

Skindex-16-

Skindex 16 16,17-

Scoring (0=never bothered to 6=always bothered), Total 0 to 96

Symptom Subscale

- Skin itching 1.
- Skin burning or stinging 2.
- Skin hurting 3.
- Skin irritated 4.

Emotional Subscale

- 5. Persistence or recurrence of condition
- 6. Worry about condition
- Appearance of skin 7.
- 8. Frustration about skin
- Embarrassment about skin 9.
- Annoyed about skin 10.
- Feeling depressed 11.

Functional Subscale

- 12. Effect of skin on interaction with others
- Effect of skin on desire to be with people 13.
- Skin making it hard to show affection Effect of skin on daily activity 14.
- 15.
- Skin making it hard to work/have enjoyment 16.

16 Dermatolo	gy Life Qual	lity Index (DI	LQI)
MRN:			Date:
			Score:
Name:			
-			re how much your LLP has affected your life eck one box for each question.
1. Over the last we Very much □	ek, how itchy, sor A lot □	e, painful or stingi A little □	ng has your skin been? Not at all □
2. Over the last wover the last work of	eek, how embarra A lot □	assed or self cons A little □	scious have you been because of your rash? Not at all □
3. Over the last we Very much □	eek, how much ha A lot □	s your skin interfe A little □	ered with you going shopping or looking after your home or garden? Not at all □ Not relevant □
Over the last week, howear?	ow much has you	r skin influenced tl	he clothes you Very much
□ A lot □ relevant □	A little □	Not at all □	Not
		•	ed any social or leasiure activity? Not at all □ Not relevant □
5. Over the last week do any sport?	, how much has y	our skin made it	difficult for you to Very much □
A lot □	A little □	Not at all □	Not relevant
6. Over the last week □ No □ been a problem at wo	If "No" over	•	vorking or studying? Yes ow much has your skin
A lot □	A little □	Not at all □	

Over the last week,	how much has y	our skin created ہ	oroblems with your	partner or any of your close friends o	r relatives?
Very much □	A lot □	A little □	Not at all □	Not relevant □	
8. Over the last week	, how much has	your skin caused	any sexual difficu	ties?	
Very much □	A lot □	A little □	Not at all □	Not relevant □	
9. Over the last week messy, or by taking u		a problem has the	e treatment for you	ır skin been, for example by making	your home
Very much □	A lot □	A little □	Not at all □	Not relevant □	
Very much □	A lot □	A little □	Not at all □		
A little □	Not at al

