Objectives	To evaluate the safety and efficacy of Deucravacitinib (BMS-986165) in Lichen Planopilaris and Frontal Fibrosing Alopecia as assessed by the change in Physician Global Assessment (PGA) of skin, oral mucosa, and hair, LPPAI. To predict responses through the identification of unique biomarkers of LPP at week 0 and utilizing bulk, spatial, and single-cell RNA sequencing					
Number of Subjects	22 (12 in cohort A and 10 in cohort B)					
Diagnosis and Main Inclusion Criteria	Adult patients with active LPP 1) 18 years old or older at time of consent 2) Biopsy proven diagnosis of LPP					
Study Product, Dose, Route, Regimen	Deucravacitinib (BMS-986165) 6 mg orally administrated, twice daily (Cohort A) and 6 mg orally QD (Cohort B).					
Duration of Administration	Drug will be administered from Day 0 through Week 24.					
Reference therapy	None					
Statistical Methodology	The statistical analysis will provide descriptive summary statistics for categorical and continuous outcomes. Categorical variables will be described by their count and proportion of occurrence while continuous, normally distributed variables will be described by their mean and standard deviation; and continuous, non-normally distributed variables will be described by their median and range.					

1 Introduction

This document is a protocol for a human research study. This study will be carried out in accordance with the applicable United States government regulations and Mayo Clinic research policies and procedures.

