
The risks of drawing blood include pain, bruising, lightheadedness, and/or fainting, or rarely, infection at the site of the needle stick.

Other:

As with all research, there is a chance that confidentiality could be compromised; however, we take precautions to minimize this risk.

2 Study Objectives

Primary Objective:

To determine the efficacy of Deucravacitinib (BMS-986165) as measured by Lichen Planopilaris Activity Index (LPPAI) score for overall response (Complete and partial responders) at week 24. Percent reduction of baseline LPPAI score after 24 weeks of treatment is defined as follows:

- Complete response: LPPAI reduction greater than 85% from baseline score.
- Partial response: LPPAI reduction between 25-85% from baseline score.
- Non-response: LPPAI reduction of less than 25% from baseline score.

The Lichen Planopilaris Activity Index (LPPAI) is a standardized validated quantitative measure of disease activity [12]. LPPAI score (0-10) is calculated as follows: (pruritus + pain + burning)/3 + (scalp erythema + perifollicular erythema + perifollicular scale)/3 + 2.5 (pull test) + 1.5 (spreading/2). Symptoms and signs are graded on a 4-point scale with 0 = absent, 1 = mild, 2 = moderate, and 3 =severe. Clinical progression and a positive hair pull test are graded 1 =yes; 0 =no.

Secondary Objective:

To determine the efficacy of Deucravactinib (BMS 986165)) as measured by the changes in PGA of scalp, DQLI score, VAS, VRS, NRS, and Skindex-16.(weeks 0 to 4, weeks 4 to 8, weeks 0 to 8, weeks 8 to 12, weeks 0 to 12, weeks 12 to 16, weeks 0 to 16, weeks 16 to 20, weeks 20 to 24, and weeks 0 to 24).

Exploratory Objectives:

To predict responses and examine the pharmacodynamics of treatment through the identification of unique biomarkers and transcriptomic changes of LPP at week 0 and utilizing single-cell RNA sequencing on responsive and non-responsive tissue at week 4 to correlate these biomarkers with measures of global response:

3 Study Design

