3.1 General Description

This is a single center, exploratory, open-label, single-arm design study of 22 patients. Adult patients with biopsy proven LPP with active disease will be treated Deucravacitinib (BMS-986165) for 24 weeks. Multiple safety studies have been conducted with Deucravacitinib (BMS-986165) (see Safety) and a dose of 6 mg BID (Cohort A) and dose of 6 mg QD (Cohort B) is deemed safe. (Investigator's Brochure)

Individuals over the age of 18 with biopsy proven LPP will be eligible. Individuals must have active disease at baseline. Patients with end-stage scarring hair loss but without significant active disease will be excluded. Prior treatment will be allowed; however, a washout period of 2 weeks for topical and 4 weeks or longer (see Table 1) for systemic agents is required. At the washout period, individuals will undergo evaluation with LPPAI, PGA, DQLI, VAS, VRS, NRS, and Skindex-16. The scalp lesions will be photographed.

Individuals will then initiate treatment with Deucravacitinib (BMS-986165) 6 mg twice daily (Cohort A) and dose of 6mg QD (Cohort B) will be evaluated every 4 weeks and assessed by LPPAI, PGA between weeks 0-24 (see Appendix). Week 24 will be the primary endpoint. Therapy will be stopped and the individuals will be evaluated at week 28 after an observation period of 4 weeks and assessed by the aforementioned assessment tools. Laboratory and safety monitoring will occur at weeks 0, 2, 4, 8, 12, 16, 20, 24, and 28. 3D Photographs will be taken at weeks 0, 2, 4, 8, 12, 16, 20, 24, and 28. Up close photos will be taken of the disease.

A 4 mm punch biopsy of the scalp will be collected for all subjects. Blood collection will include the isolation at week 0, 2, 4, 8, 12, 16, 20, 24, and 28. Blood will be drawn into 5mL vials and subsequently separated. The serum and cell pellet will be stored for future analysis.

Normal patient controls will be obtained from archival tissue collected from normal scalp biopsies at the University of Michigan (Cohort A only). Tissue (up to a 4 mm biopsy sample) will be obtained for analysis from the University of Michigan biobank (Cohort A only). The University of Michigan Biobank has IRB approval for the collection, processing, and storage of samples. All tissue analyses will be conducted at the University of Michigan. Only deidentified data for the control samples will be shared with Mayo Clinic.

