Single cell RNA sequencing will be performed at week 0 and week 4 (Cohort A only). A total of up to 30 (14 pre-treatment, 14 post treatment, 4 controls) skin samples will be completed for single cell sequencing (Cohort A only). Bulk RNA sequencing will be completed on up to 30 tissue samples (14 pre-treatment, 14 post treatment, 4 healthy controls) (Cohort A only). Spatial RNA sequencing will be completed on 28 tissue samples (14 pre-treatment, 14 post treatment) (Cohort A only).

Bulk, single-cell and spatial RNA Transcriptome Sequencing: Samples will be prepped and analyzed per bulk, spatial, and single-cell RNA sequencing standard operating procedures of the University of Michigan genomics lab (Cohort A only). Processing and operating protocols are as follows:

Bulk, Single Cell and Spacial RNA Sequencing

Biopsy Processing for bulk and spatial sequencing:

Biopsies will be collected following standard Mayo BAP procedures. Immediately following collection, tissue biopsies will be submerged in formalin. Formalin samples will be shipped to the University of Michigan.

Biopsy Processing for single cell sequencing:

Biopsies will be collected following standard Mayo BAP procedures. Immediately following collection, tissue biopsies will be submerged and frozen in Cryostor CS10 media at a rate of -1°C/minute and stored at -80C. Frozen samples will be shipped within 2 weeks of collection to the University of Michigan. Upon receipt, samples will be stored at -80C until time of processing for single cell sequencing.

Single Cell Sequencing:

Cells will be isolated from cutaneous punch biopsies using collagenase or trypsin containing DNase. Epidermis and dermis are first isolated from one another and then processed separately. Cell quality and quantity will be assessed using Trypan Blue exclusion. Samples with >75% viability will be sequenced without additional cleanup steps. Samples with <75% viability will be further processed to increase concentration of viable cells prior to sequencing.

Primary and Secondary Measures:

All efficacy assessments will be performed prior to the administration of study treatment at each visit. The recommended order and the overall outline of measurements for the efficacy assessments are described below.

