Primary Outcome measures: The primary outcome measure will be LLPAI score for overall response between week 0 and week 24. Change in LLPAI will also be assessed week 0 to week 2, weeks 0 to 4, weeks 4 to 8, weeks 0 to 8, weeks 8 to 12, weeks 0 to 12, weeks 12 to 16, weeks 0 to 16, weeks 16 to 20, weeks 0 to 20, w change in NRS (week 0 to week 2, weeks 0 to 4, weeks 4 to 8, weeks 0 to 8, weeks 8 to 12, weeks 0 to 12, weeks 12 to 16, weeks 0 to 16, weeks 0 to 20, weeks 0 to 24, week 20 to 24, week 0 to 28, weeks 24 to 28, weeks 0 to 28), and change in Skindex-16 (week 0 to week 2, weeks 0 to 4, weeks 4 to 8, weeks 0 to 8, weeks 8 to 12, weeks 0 to 12, weeks 12 to 16, weeks 0 to 16, weeks 16 to 20, weeks 0 to 20, weeks 0 to 24, week 20 to 24, week 0 to 28, weeks 0

Exploratory Outcome Measures: To predict responses and examine the pharmacodynamics of treatment through the identification of unique biomarkers and transcriptomic changes of LPP at week 0, and utilizing RNA sequencing on responsive and non-responsive tissue at week 4 to correlate these biomarkers with measures of global response: LPPAI, PGA.

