3.5 Secondary Study Endpoints

Change in PGA score (week 24), change in the Dermatology-QLI score (week 24), change in VRS (week 24), change in NRS (week 24), and change in Skindex-16 (week 24).

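### The PGA already rates change from baseline, yet it is scored before treatment and analysed as a change score; the endpoint should be the week-24 grade itself

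*Combined protocol and SAP*

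**What the plan says.** The appendix defines the PGA in seven grades. Grades 0 to 4 are bands of percent improvement, Grade 6 is worsening of 25% or more, and between them sits "Grade 5 No change; disease has not changed from baseline condition (+/-<25%) SD". Supplemental 1 describes the PGA as a physician's measure of overall response to treatment. The documents define no PGA of current severity.

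The same instrument is scheduled before treatment. Section 3.1 states: "At the washout period, individuals will undergo evaluation with LPPAI, PGA, DQLI". Table 3 marks it at Day 0 (not at Screening), and section 6.2 lists it among the Day 0 procedures. Section 3.1 adds: "All efficacy assessments will be performed prior to the administration of study treatment at each visit".

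The analysis is worded as change throughout. Section 3.5 lists first "Change in PGA score (week 24"; the Study Summary objective reads "as assessed by the change in Physician Global Assessment (PGA"; and the secondary objective in section 2 is efficacy "as measured by the changes in PGA of scalp" and of the other secondary scales, over ten intervals ending "weeks 16 to 20, weeks 20 to 24, and weeks 0 to 24". Section 7.2 assigns no summary or test to the PGA by name, apart from individual plots of the PGA score over time.

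**The concern.** A rating that is itself a change from baseline needs a named baseline visit, and it should not be differenced again. The plan leaves the baseline visit unnamed, asks for the rating before there is any response to rate, and then asks for a change in it. Two analysts could derive different numbers under the same label, and a reader could not tell whether a reported change of -2 is a relabelled week-24 grade or a difference between two ratings.

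At stake is the meaning of the first-listed secondary endpoint. Section 7.2 says the study is for estimation only, so the issue is what the reported PGA estimate means, not a decision rule.

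**Working it through.** The plan states no PGA figure to reproduce, so the check sets the scale against the schedule and the intervals.

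**Inputs from the documents.** Appendix cut-offs in percent improvement: Grade 0 = 100; Grade 1 = 90 to <100; Grade 2 = 75 to <90; Grade 3 = 50 to <75; Grade 4 = 25 to <50; Grade 5 = within ±25; Grade 6 = worse by 25 or more. Intervals in section 2 that start at week 0: 0-4, 0-8, 0-12, 0-16, 0-24. Between later visits: 4-8, 8-12, 12-16, 16-20, 20-24.

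**1. Baseline is Day 0.** The Day 0 grade is then 5 for every patient, if it is given at all. Change = later grade - 5, so the possible values are -5, -4, -3, -2, -1, 0 and +1. Subtracting a constant leaves the spread and ranks untouched. On 22 invented grades, a paired Wilcoxon test against Day 0 and a one-sample signed-rank test about 5 gave the same result (statistic 12.0, p = 0.0013).

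**2. Baseline is washout.** Day 0 may then differ from 5, because section 3.3 allows 1 to 4 weeks for screening and washout. A change from Day 0 becomes a difference of two ratings, each made against washout, and could run from 0 - 6 = -6 to 6 - 0 = +6. The washout PGA is now the entry that is 5 for everyone or has no meaning. The lack of a PGA in Table 3's Screening column points to case 1 but does not settle it.

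**3. Visit-to-visit changes.** Band widths in percentage points are just under 50 (Grade 5), 25 (Grades 4 and 3), 15 (Grade 2), 10 (Grade 1) and a single value (Grade 0).
- A step from 5 to 4 can be anything up to just under 50 - (-25) = 75 points.
- A step from 1 to 0 is at most 100 - 90 = 10 points.
- A move of nearly 50 points inside Grade 5 shows as no change.

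**4. What a mean change would do, if one were reported.** Take case 1 and two patients with equal and opposite percent changes.
- 30% each way: (-1 + 1)/2 = 0.
- 60% each way: (-2 + 1)/2 = -0.5.
- 95% each way: (-4 + 1)/2 = -1.5.

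For a group, assume percent improvement X is normal with mean 0. The documents give no SD, so a range is shown. By symmetry the first improvement step cancels the single worsening step, leaving

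mean change = -[P(X≥50) + P(X≥75) + P(X≥90) + P(X≥100)].

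At SD 35 this is -(0.0766 + 0.0161 + 0.0051 + 0.0021) = -0.100.

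| Assumed SD (points) | 25 | 35 | 45 | 55 |
|---|---|---|---|---|
| Mean change (grades) | -0.024 | -0.100 | -0.217 | -0.353 |
| Same, improvement capped at 100% and mean re-set to 0 | -0.024 | -0.095 | -0.188 | -0.282 |

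The population median grade is 5 (change 0) in every setting. Counts per grade do not involve the subtraction.

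**5. Precision of the proposed proportion at Grades 0-3.** Exact binomial 95% intervals at an observed 50%: 5/10, 18.7-81.3%; 6/12, 21.1-78.9%; 11/22, 28.2-71.8%.

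**The case against.** The best defence is that nothing is lost. If Day 0 is 5 for everyone, the change is a one-to-one relabelling of the week-24 grade, and a paired test against Day 0 is a coherent one-sample test against no change. This stands. A reader might infer that the week-24 PGA is uninterpretable; the documents do not support that, because the week-24 grade is already the change measure.

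A reader might also infer that the plan biases the PGA towards benefit. That is not supported either. Section 7.2 reserves mean and SD for normally distributed continuous variables and otherwise gives median and range, or counts and proportions. A seven-grade rating fits the latter two better, and neither carries the lean. The size of the lean also rests on an SD and a distribution that the documents do not give.

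A third tempting inference is that the Day 0 grade must be 5. It need not be if raters use washout as the reference.

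Two further points have weight. The outcome list in section 3.1 is broken in the text available ("weeks 0 to 20, w change in NRS"), so a PGA entry may have been lost; the conclusion therefore rests only on the intact scale, schedule and objectives. The unequal bands belong to a scale that the protocol takes from cited sources. They are no fault in themselves and matter only because grades are to be subtracted between visits.

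Finally, the section 3.5 wording alone could simply mean the week-24 grade. The Day 0 scoring and the week-0 intervals in section 2 do not fit that reading.

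**Conclusion.** The point holds as a mis-specified secondary endpoint of minor priority. The only PGA defined is a rating of change from baseline; it is scheduled before treatment, its baseline visit is not named in any legible text, and it is analysed as a change. With Day 0 as baseline, five of the ten listed intervals relabel the later grade on a -5 to +1 scale. The other five subtract change ratings whose one-grade steps range from at most 10 points to just under 75. With washout as baseline, the meaningless entry moves to washout and the week-0 intervals also become differences of change ratings.

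The -5 to +1 range rests on Day 0 being the baseline, which Table 3 suggests but no text states. The lean of 0.02 to 0.35 grades rests on a mean being reported and on the assumed SDs. The primary LPPAI responder endpoint and the sample size of 22 are unaffected.

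**What to change.** - Name Day 0 as the baseline to which every PGA grade refers.
- Remove the PGA from the washout and Day 0 assessments, and remove the PGA change scores.
- In section 3.5, replace the PGA change endpoint with *PGA grade at week 24*, and align the Study Summary objective and section 2.
- In section 7.2, report the count and proportion in each Grade 0-6 at week 24, and the proportion at Grades 0-3 (the appendix's complete plus partial response) with the exact binomial 95% interval already planned there for response rates.
- State that Grades 0-3 require at least 50% improvement, whereas LPPAI partial response in section 2 starts at 25%, so the two responder rates are not interchangeable.
- Describe other visits by their grade distribution. The individual PGA plots can stay, starting at week 2.

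The cost is wording in the endpoint, objectives, schedule and analysis text. No new data are needed and there are fewer assessments before treatment. What is given up is a mean-change summary for the PGA. Section 1.1 already reports preliminary Cohort A results on the PGA; those grades stay usable, but the sponsor should confirm which visit the raters took as baseline. A static severity PGA is not needed for this fix; it would be a new scale, and patients already assessed would have no Day 0 score on it.
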